3.2 Endpoints

Primary Efficacy Endpoint

The primary efficacy endpoint is whether the subject is an overall responder.

A subject is an 'overall responder' if they have reported an improvement in their weekly (Cohort specific) symptoms for \geq 50% of the treatment period (4 out of 8 weeks).

	IBS-C	IBS-D	
Primary Endpoint Responder Symptom Definition	Abdominal Pain Intensity Decrease in weekly average of worst abdominal pain in the past 24 hours score of at least 30% compared with baseline	Abdominal Pain Intensity Decrease in weekly average of worst abdominal pain in past 24 hours score of at least 30% compared with baseline	
	And Stool Frequency	and Stool Consistency (BSS)	
	Increase of 1 or more Complete spontaneous bowel movements (CSBM) per week compared with baseline.	Decrease at least 50% in the proportion of days per week with at least one stool that has a consistency of Type 6 or 7 compared with baseline.	

Secondary Efficacy Endpoints

- Subject global assessment of relief
- Stool consistency/frequency
- IBS-QOL
- IBS-SSS
- HADS

Exploratory Endpoints

Safety Endpoints

- Incidence, nature, severity, relatedness, seriousness, expectedness and outcome of adverse events
- Haematology and blood chemistry assessments
- Vital signs

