4.2 Study Design

4.2.1 Overall Study Design

Subjects who are potentially suitable for the study will be identified from current patient lists at appropriate gastroenterology clinics and or by advertisement. Subjects will be approached to determine if they are interested and willing to participate. The investigative sites will provide interested subjects with a 'Research Study Information and Informed Consent Form' and they will be booked in for the initial screening visit when consent will be obtained, and the Subjects will be asked to sign the Consent Form

Screening Visit (Up to 4 weeks before dosing starts Day -28 to Day -1)

Following completion of the study consent form, subjects will be screened against the protocol requirements, and a medical history and concomitant medications will be documented, a full physical examination will be performed, and bloods will be drawn for haematology, serum biochemistry and viral serology. Vital signs (pulse, blood pressure, respiratory rate and body temperature) will be assessed and recorded, and a 12 lead ECG will be taken. Women of child bearing potential will have a serum pregnancy test. Height and weight will be measured, and if subjects fulfil all the eligibility criteria at this part of the Screening process they will be provided with a Smartphone containing an 'Electronic Clinical Outcomes Assessment' (eCOA) App and will be provided with training and instructions on how to use the device. At this Visit they will complete the IBS-Symptom Severity Score (SSS) on a tablet device during the clinic visit.

The subject will be asked to take the smart phone home and complete the following assessments daily over a 7-day period. These assessments will need to be completed prior to attending the clinic for their Baseline Visit 1

- An abdominal pain intensity rating scale daily
- Bowel movements, Stool consistency/frequency daily and laxative use
 - If no bowel movements, this should be recorded as zero

The subject will need to ensure they complete these two assessments at least one day prior to the day next clinic visit. As soon as the subjects have completed their assessments and click submit on the smartphone, their data will be sent to the hub for review by the investigator and study team. The same smartphone will be used throughout the study for all patient reported outcome assessments.

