5.1 Inclusion Criteria

All subjects must meet all the following inclusion criteria:

- 1. Written consent on an Institutional Review Board (IRB)/ Independent Ethics Committee (IEC) approved ICF before any study specific evaluation
- 2. Males and Females between 18 and 70 years of age
- 3. Body Mass Index (BMI): 18-39 kg/m²
- 4. Having IBS-C or IBS-D as defined by Rome IV, including Subtype Classification as defined per Table 2

Recurrent abdominal pain on average, at least 1 day/week in the last 3 months associated with two or more of the following criteria:

• Related to defecation

- Associated with a change in frequency of stool
- Associated with a change in form (appearance) of stool

The above criteria must be met for the last 3 months with symptom onset at least 6 months prior to diagnosis.

IBS-C and IBS-D subtypes will be further classified as follows:

Table 3:

IBS-C	IBS-D
□ Abdominal Pain Intensity: weekly average of worst daily (in past 24 hours) abdominal pain score of > 3.0 on a 0 to 10-point scale	\Box Abdominal Pain Intensity: weekly average of worst daily (in past 24 hours) abdominal pain score of > 3.0 on a 0 to 10-point scale
	And
And	
□ Stool Frequency: more than 25% of bowel movements with a consistency of Type 1 or Type 2 Bristol stool chart and less than 25% of bowel movements with Bristol stool form Type 6 or Type 7. Subject must have fewer than 3 CSBMs ¹ within a one week period (7 days)	□ Stool Consistency: more than 25% of bowel movements with a consistency of Type 6 or Type 7 Bristol stool chart and less than 25% of bowel movements with Bristol stool form Type 1 or Type 2. Subjects must have at least one Type 6 or Type 7 bowel movements on at least four days within a one week period (7 days).

*Stool types based on Bristol Stool Chart; Hard stools -Type 1 and 2; Soft stools – Type 6 and 7 (see Appendix 3). Source: (https://irritablebowelsyndrome.net/clinical/new-rome-iv-diagnostic-criteria/) (see Appendix 6) ¹ CSBM defined as a bowel movement that is both complete and spontaneous. Bowel movements where laxative use is recorded in the concomitant medication questions in a 24 hour period, by IBS-C subjects will not be counted as CSBMs when subtyping for randomisation.

- Have a moderate or severe IBS symptom severity score ; ≥175 at the screening visit as defined by IBS-SSS. A tolerance of -10% (≥ an IBS-SSS score of 157.5) will be allowable at the Baseline (Visit 1).
- 5.2 Exclusion Criteria

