Subjects will be asked to complete a quality of life questionnaire consisting of 34 questions with a five-point response. The individual responses to the 34 items are summed and averaged for a total score and then transformed to a 0-100 scale for ease of interpretation with higher scores indicating better IBS specific quality of life. Once subjects are randomised they will be asked to record their score on their smartphone at each clinic visit or within 24hrs prior to the Clinic Visit.

Hospital Anxiety and Depression Score (HADS) (Appendix 2)

Subjects will be asked to complete HADS which is a 14-item scale that generates ordinal data. Seven of the items relate to anxiety and 7 relate to depression. Each item is scored from 0-3 so a subject can score 0 to 21 for either anxiety or depression. Once subjects are randomised they will be asked to complete this questionnaire on their smartphone at each clinic visit or within 24hrs prior to the Clinic Visit.

Bristol Stool Chart

Subjects will be asked to record stool frequency and consistency. Stool types will be based on the Bristol Stool Chart (Appendix 3). This data will be recorded daily for a 7-day period up to Baseline (Visit 1) to allow Subject to be classified into Cohorts of IBS sub-types. Once subjects are randomised they will be asked to record their stool frequency daily up to 10 bowel movements per day and score each stool type on their smartphone. No bowel movements in any given day will also be recorded.

Stool frequency will be defined as a sum of weekly CSBMs. Stool frequency will be recorded using the following question: "How many times did you open your bowels during the past 24 hours? If you have not had any bowel movements today, please enter 0." Subjects will be reminded to rate all of their bowel movements in the Bristol Stool Chart before answering the question. CSBMs will be determined by absence of laxative use recorded in concomitant medication questions for the same 24 hour period.

IBS Symptom Severity Score (SSS) (Appendix 4)

Subjects will be asked to complete a questionnaire on severity of abdominal distension, severity of abdominal pain, frequency of abdominal pain, dissatisfaction with bowel habits, and interference of IBS symptoms with daily life. A score ranging from 0 (no symptoms) to 500 (maximum severity) can be achieved as mild (74-174), moderate (175-299) or severe (>300) IBS symptoms.

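### The IBS-C primary component is called a CSBM response, but the only stated derivation ignores completeness and the SAP gives none

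*Protocol*

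**What the plan says.** Protocol 3.2 sets the IBS-C stool component as "Increase of 1 or more Complete spontaneous bowel movements (CSBM) per week compared with baseline". The footnote to the subtype table in protocol 5.1 has "CSBM defined as a bowel movement that is both complete and spontaneous". It then adds a laxative exclusion with a narrow scope: movements with recorded laxative use "by IBS-C subjects will not be counted as CSBMs when subtyping for randomisation". IBS-C entry requires fewer than 3 CSBMs in 7 days.

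Protocol 7.1 gives the working rule. It states "Stool frequency will be defined as a sum of weekly CSBMs", collects the count with the question "How many times did you open your bowels during the past 24 hours", and ends with "CSBMs will be determined by absence of laxative use recorded in concomitant medication questions for the same 24 hour period". It also says "Subjects will be reminded to rate all of their bowel movements in the Bristol Stool Chart before answering the question".

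SAP 10.1.1 names CSBMs as the response variable. It then describes a once-daily count of bowel movements and a stool frequency scaled by 7. SAP 10.2 lists only stool frequency for baseline. SAP 10.4 says Bristol data are expected to be missing on a date with zero CSBMs, and that such a day still counts toward the four-day minimum. SAP 11.3.2 summarises stool frequency and CSBMs as separate quantities.

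**The concern.** A laxative filter can establish that a movement was spontaneous. It cannot establish that it was complete. If completeness was not recorded, or was recorded but is not used, a positive IBS-C result shows response on laxative-free movements plus pain, which is not the response the endpoint names. The same variable enters IBS-C eligibility, the baseline value and the IBS-C covariate in SAP 10.3.

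The SAP does not settle the matter. The double independent programming in SAP 6 may reveal that two programmers read the text differently, but it cannot say which reading was intended.

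**Working it through.** **The plan's own figure.** Protocol 10.2 claims at least 80% power with 125 per arm, 40% versus 55%, one-sided alpha 0.10 and the Yates correction. Exact binomial enumeration gives 82.5%, so the claim reproduces. This point does not alter it: the documents give no rate of incomplete movements from which a corrected response rate or power could be derived.

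**Three possible counts.** For one subject-week, let B be all movements, L those with no laxative in the same 24 hours, and C those in L that were also complete. Then C ≤ L ≤ B. Protocol 5.1 defines C. Protocol 7.1 computes L. A loose reading of SAP 10.1.1 gives B.

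**Is completeness collected daily?** Six places describe the daily bowel diary: protocol 4.2.1 at Screening ("Bowel movements, Stool consistency/frequency daily and laxative use"), Baseline, Visit 2, End of Treatment and Follow-up, and SAP 4.

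| Item | Named in |
|---|---|
| Laxative use | 6 of 6 |
| Spontaneity | 1 of 6 (Baseline) |
| Completeness | 0 of 6 |

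The only question on incomplete emptying is item 7e of IBS-SSS Part 2 (protocol Appendix 4). It is answered at clinic visits, not per movement, and SAP 10.1.2.4 does not score Part 2.

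**Eligibility (fewer than 3).** Because C ≤ L, L < 3 implies C < 3. On this criterion the 7.1 rule can only exclude extra subjects. Example: 5 laxative-free movements, 2 of them complete, give C = 2 (meets the criterion) and L = 5 (does not).

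**Weekly response (gain of at least 1).** Either direction is possible.

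- Case A: 2 laxative-free movements (1 complete) become 3 (1 complete). The 7.1 rule gives 3 − 2 = +1, improved. The 5.1 definition gives 1 − 1 = 0, not improved.
- Case B: 2 (0 complete) become 2 (2 complete). The 7.1 rule gives 2 − 2 = 0, not improved. The 5.1 definition gives 2 − 0 = +2, improved.

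**Scale, by assumption only.** Suppose a fraction q of laxative-free movements is complete, the same at baseline and on treatment. The documents give no value, so q = 0.25 to 0.75 is shown. Change in C = q × change in L.

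| q | CSBM gain from +1 laxative-free movement | Extra laxative-free movements for +1 CSBM (1/q) |
|---|---|---|
| 0.25 | 0.25 | 4.00 |
| 0.50 | 0.50 | 2.00 |
| 0.75 | 0.75 | 1.33 |

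A constant q rules out Case B, in which the fraction itself changes, so the table covers only part of the problem.

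**SAP 10.4.** On a laxative day with 2 stools, the 7.1 rule gives 0 CSBMs, yet 2 Bristol ratings are expected because all movements are to be rated. The SAP's expectation is correct only if every movement is a CSBM. A day of this kind with ratings is not lost, since it still counts. A day whose ratings are genuinely missing is accepted as well.

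**The case against.** The strongest reply is that the diary lists are abbreviated visit summaries. They are not independent: SAP 4 largely repeats the protocol's Screening text. Spontaneity appears in only one of them although the same device is used throughout, so the absence of completeness shows little. Protocol 10.7 and SAP 10.4 speak of daily CSBM records, and SAP 11.3.2 keeps CSBMs apart from stool frequency, which is compatible with a distinct CSBM variable. The SAP is written from the protocol and its Section 13 lists no change here, so protocol 7.1 governs and the all-movements reading is strained. The 10.4 sentence looks like a wording slip: Bristol type is not part of the IBS-C responder definition, and in IBS-D, under the 7.1 rule, harm needs a laxative day with stools and missing ratings.

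Much of this stands as a limit. The tally is supporting evidence; the main evidence is the question and rule in 7.1. The eCOA screens, the annotated eCRF and the table specifications are not available, so the claim is that completeness is not documented, not that it was not collected. The 10.4 problem is smaller than the CSBM definition, and its frequency is unknown.

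The core is not answered. References to CSBM records do not show that completeness was asked, because 7.1 produces a CSBM count without it. If 7.1 governs, the component is the laxative-free count, which is not what 5.1 defines.

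**Conclusion.** The plan is wrong as written on this point and should be corrected before database lock. Protocol 5.1 and 7.1 disagree on what a CSBM is, the SAP does not choose between them, and the SAP 10.4 expectation conflicts with the protocol's own rule.

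The definition concerns Cohort C. Its 250 planned subjects are the cohort size, not a count of subjects misclassified. The evaluable-week wording has no cohort limit and reaches both cohorts. The effect on response rates cannot be estimated from the documents; the worked cases show only that readings can differ in either direction. The measure is the same in both blinded arms, so no between-arm bias is claimed. Confidence is moderate, because the deployed diary items could show that completeness was captured. In that case the remaining defect would be the missing derivation.

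**What to change.** Before database lock, have staff with no access to the unblinded interim results (SAP 10.5) check the deployed eCOA items. Then fix and date one derivation.

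- **If completeness was captured:** define a CSBM as a complete movement with no laxative in the same 24 hours, and reconcile this with the spontaneity item listed at Baseline in protocol 4.2.1.
- **If it was not:** label the component *spontaneous (laxative-free) bowel movements* and make no claim of CSBM response.

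Use the same derivation for the description of eligibility, for baseline and treatment weeks (SAP 10.1.1, 10.2, 10.4, 11.3.2) and for the IBS-C covariate (10.3). State the multiplication by 7 for baseline too, since 10.2 gives a conversion only for consistency. Change 10.4 so that Bristol data are expected to be missing only when the number of bowel movements is zero, in both cohorts.

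Add an entry to SAP Section 13. Because the protocol contradicts itself, either choice departs from part of it: from 7.1 in the first case, from 5.1 and 3.2 in the second.

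No diary change is proposed, because protocol Appendix 13 says the primary-endpoint assessments are complete. The cost is one specification check, a few sentences of SAP revision and one Section 13 entry. The possible downside is a less favourable endpoint label for IBS-C.

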7.2 Laboratory Assessments

A Laboratory Manual will be prepared to document the address and contact numbers for all laboratories involved in the study and the collection, processing, shipment, storage and reporting procedures for all samples.

7.2.1 Safety Assessments:

Refer to Table 1: Schedule of Assessments and Procedures for sample collection timepoints.

Blood Samples:

Haematology:

Haemoglobin (HGB), haematocrit (HCT), mean cell volume (MCV), mean cell haemoglobin (MCH), mean cell haemoglobin concentration (MCHC), red blood cells (RBC), C-reactive Protein (CRP), white cell count (WCC) and platelets (PLT). Differential white cell count will include

neutrophils, lymphocytes, eosinophils, basophils and monocytes as absolute values and percentages.

Clinical Chemistry:

Total protein (TP), albumin (ALB), total bilirubin (BIL-T), alanine transaminase (ALT), aspartate transaminase (AST), gamma-glutamyl transferase (GGT), glucose (GLU), sodium (NA), potassium (K), bicarbonate (HCO₃), creatinine (CREA), urea, calcium (Ca), phosphate (PO₄), globulin.

Serology:

At screening the analyses will also include HIV-1 & HIV-2, Hepatitis B surface antigen (HBsAg), a Hepatitis B surface antibody (Anti-HBs), a Hepatitis core antibody test (anti-HBc) and Hepatitis C.

Pregnancy test:

A serum pregnancy test will be conducted for all female subjects at the screening visit.

Urine Samples:

A fresh urine sample will be collected for a pregnancy test in all female subjects at Baseline (Visit 1), Visit 2, End of Treatment and Follow-up (dipstick testing).

7.2.2 Exploratory Assessments

7.2.3 Total Blood Volumes

The total amount of blood taken from each subject during the study will be approximately 150 ml

7.2.4 Laboratory Manual

A Laboratory Manual will be prepared to document the address and contact numbers for all laboratories involved in the study and the collection, processing, shipment, storage and reporting procedures for all samples.

8 SAFETY DATA COLLECTION, RECORDING AND REPORTING

8.1 Responsibilities

The Safety and Medical Management Plan details the roles and responsibilities, Serious Adverse event processing, reporting of safety data, SAE reconciliation and Medical monitoring for this study.

8.2 Definitions

8.2.1 Adverse Events

An adverse event is any untoward medical occurrence in a subject administered study medication and which does not necessarily have to have a causal relationship with this treatment. Abnormal laboratory values or test results constitute adverse events only if they induce clinical signs or symptoms, are considered clinically significant, or require therapy.

The occurrence of adverse events should be sought by non-direct questioning of the subject at baseline (pre-dose) Adverse events will be checked at every clinic visit. Adverse events may be detected when they are volunteered by the subject or through physical examination, laboratory test, or other assessments. All adverse events must be recorded in the CRF with the following information:

- 1. Diagnosis: diagnosis if known, otherwise sign or symptom;
- 2. Seriousness: whether it constitutes a serious adverse event (SAE) and therefore requires reporting immediately (see Section 8.3)
- 3. Criteria for Adverse Events:

Mild: Asymptomatic or mild symptoms; clinical or diagnostic observations only; intervention not indicated

Moderate: Moderate; minimal, local or non-invasive intervention indicated; limiting ageappropriate instrumental ADL (Activities of Daily Living)

Severe: Severe or medically significant but not immediately life-threatening; hospitalization or prolongation of existing hospitalization indicated; limiting self-care ADL (Activities of Daily Living)

- 4. Relatedness: relationship to the study medication will be assessed as reasonable possibility of being related or no reasonable possibility of being related;
- 5. Duration: start and end dates or, if continuing, at final examination;
- 6. Action: any action taken to manage it (none, dosing interrupted, dosing stopped, other, medication);

7. Outcome: the outcome (completely recovered, recovered with sequelae, condition improving, condition still present and unchanged, condition deteriorated, death).

8.2.2 Serious Adverse Events

A serious adverse event is defined as an event which:

- results in death
- is life-threatening
- requires hospitalisation or prolongation of hospitalisation
- results in persistent or significant disability or incapacity
- consists of a congenital anomaly or birth defect
- is a medically important event

All adverse events should be treated appropriately. Treatment may include one or more of the following: no action taken (i.e., further observation only); study medication discontinued due to this adverse event; concomitant medication given; non-drug therapy given. The action taken to treat the adverse event or resolve the adverse incident should be recorded on the CRF.

Once an adverse event is detected, it should be followed until its resolution. The suspected relationship to the study medication, the interventions required to treat it and the outcome must be recorded in the CRF.

8.3 Serious Adverse Event Reporting

A Serious Adverse Event (SAE) Form must be completed for every SAE, regardless of suspected causality, occurring after protocol-specified procedures begin after signing the consent form until 4 weeks after the End of Treatment Visit and must be reported within 24 hours of the investigative site becoming aware of the event and ideally within 24 hours of its occurrence. The Safety and Medical Management Plan will provide full details.

Any SAEs experienced after this 4-week period should only be reported to if the Investigator suspects a causal relationship to the study medication.

Recurrent episodes, complications, or progression of the initial SAE must be reported as follow-up to the original episode, regardless of when the event occurs. This report must be submitted within 24 hours of the investigator receiving the follow-up information. An SAE that is considered completely unrelated to a previously reported one should be reported separately as a new event. If recurrence after resolution of the previous episode occurs if will be reported as a new SAE.

SAEs should be followed to resolution. Follow-up information should describe whether the event has resolved or continues, if and how it was treated, and whether the subject continued or withdrew from study participation.

If the SAE is not previously documented in the investigator's brochure and is thought to be related to the investigational study medication, then this is defined as a serious unexpected suspected adverse reaction (SUSAR). It is the responsibility of the Sponsor to determine whether a reported SAE fits the classification of a SUSAR and to inform the Investigator of their decision as soon as

possible. It is the responsibility of the Sponsor to determine whether an event requires expedited reporting and to notify the Investigators of their decision as soon as possible.

4D Pharma, or its designee, reports SAE's and/or SUSARS as required to regulatory authorities, investigators/institutions, and IRBs/IECs in compliance with all reporting requirements according to local regulations and good clinical practice.

The investigator is to notify the appropriate IRB/IEC of SAEs occurring at the site and other AE reports received from 4D Pharma or it's designee, in accordance with local procedures and statutes.

